# 10.3. Schirmer's Test (without anesthesia) (mm wetting/5min)

Schirmer's test will be performed without anesthesia, 15 minutes after corneal fluorescein test. This test will be conducted in a dimly lit room. While the patient looks upwards, the lower lid will be drawn gently downwards and temporally. The rounded bent end of a sterile strip will be inserted into the lower conjunctival sac over the temporal one-third of the lower eyelid margin. The test should be done without touching the Schirmer test strip directly with the fingers to avoid contamination by skin oils. After 5 minutes have elapsed, the Schirmer test strip will be removed and the length of the tear absorption on the strip will be measured.

# 10.4. Symptoms of ocular discomfort – Visual analogue scale

The visual analogue scale is a self-administered questionnaire and must be completed by the patient him/herself.

Itching, foreign body sensation or sandy feeling or grittiness, photophobia, burning/stinging, eye dryness, pain or ocular discomfort and sticky feeling will be assessed by the study patients using a visual analog scale from no discomfort to maximal discomfort (0 to 100%). Symptoms will be evaluated for both eyes together. (see Appendix A-III Visual Analog Scale (VAS)\_Symptoms of Ocular Discomfort).

# 10.5. Quality of Life Questionnaire: NEI-VFQ-25

The NEI-VFQ-25 is a questionnaire designed to assess health-related quality of life of patients with visual impairments. It is a short-form version of the 51-item NEI-VFQ Field Test Version, composed of 25 items relating to vision—targeted QoL grouped into the following scales: general vision (1 item), ocular pain (2 items), difficulty with near-vision activities (3 items), difficulty with distant-vision activities (3 items), limitations in social functioning due to vision (2 items), mental health symptoms due to vision (4 items), role limitations due to vision (2 items), dependency on others due to vision (3 items), driving difficulties (2 items), limitations with colour vision (1 item), limitations with peripheral vision (1 item), and one widely accepted general health item. Its reliability and validity are comparable to those of the 51-item NEI-VFQ Field Test Version (Mangione, et al 2001).

Each item is scored 0–100, with higher scores indicating better vision-targeted QOL. Items in the same scale are averaged together to create 12 scale scores. Missing items are not scored. A scale score can be generated if at least one item is answered.

The NEI-VFQ-25 represents the patient perspective on the impact of vision problems on functioning. Although not considered to be sensitive to fully capture treatment response in DED, many consider the NEI-VFQ-25 to be the standard to assess vision-targeted functioning.

In this trial the NEI-VFQ-25 will be administered in the local language. The responses to NEI-VFQ-25 are to be obtained from the patient through a self-administered format (see Appendix A-IV National Eye Institute Visual Function Questionnaire (NEI VFQ-25)).

# 10.6. Investigator and Patient Global Evaluation of Efficacy

The study investigator at each centre will conduct an overall assessment of the effect of the study device on improvement in the patients DED using the following rating scale:

• 0 = Unsatisfactory

ALOCROSS® Protocol Version 2
ALHENA study 06 July 2020

- 1 = Not very satisfactory
- 2 = Satisfactory
- 3 = Very satisfactory

The patient will rate his global evaluation of efficacy using the same rating scale.

## 11. ASSESSMENT OF SAFETY

# 11.1. Safety Parameters

## 11.1.1. Best Corrected Distance Visual Acuity (BCDVA)

Best corrected distance visual acuity will be measured with the patient's best correction and recorded in decimal.

### 11.1.2. Tonometry for measurement of Intraocular Pressure (IOP) (mmHg)

Investigator should use the same tonometer throughout the course of the study. Both eyes will be tested, with the right eye preceding the left eye. IOP will be assessed after completion of all other slit lamp examinations and dry eye assessments to avoid oxybuprocaine interference with the other examinations (Schirmer's test especially) in case a tonometry measurement needs to be performed with an anesthetic.

All tonometers must be calibrated according to manufacturer's instructions. Data need to be measured in absolute figures.

## 11.1.3. Slit lamp examination

External ocular examination and undilated biomicroscopy will be performed using a slit lamp. The patient will be seated while being examined; grading of the Meibomian glands, lids, lashes, conjunctiva, tear film debris, anterior chamber and lens will be done according the scales in Appendix A-II Slit lamp examination.

## 11.1.4. Adverse Events (AEs)

Adverse events, including ocular AEs, ocular complications, and systemic AEs will be recorded in the eCRFs. Any clinically significant change in concomitant disease or new concomitant conditions will be reported as AEs.

#### 11.1.5. Pregnancy Screen

Women of childbearing potential not using a medically acceptable, highly effective method of birth control (such as hormonal implants, injectable or oral contraceptives together with condoms, some intrauterine devices, sexual abstinence or vasectomized partner) from the Baseline visit throughout the conduct of the study treatment periods and up to 2 weeks after the study end cannot be included in the study. Post-menopausal women (two years without menstruation) do not need to use any method of birth control. For women of childbearing potential only, urine hCG pregnancy tests will be performed during the course of the study, and they will receive continued guidance with respect to the avoidance of pregnancy, as part of the Schedule of Study Procedures.

Patients must have a negative urine pregnancy test at baseline.

# 11.2. Adverse Events and Other Safety Information

#### 11.2.1. Definitions

#### **11.2.1.1.** Adverse Event (AE)

An adverse event is any untoward medical occurrence, unintended disease or injury or any untoward clinical signs (including an abnormal laboratory finding) in patients, users or other persons whether or not related to the investigational medical device.

NOTE 1: This definition includes events related to the investigational medical device or the comparator.

NOTE 2: This definition includes events related to the procedures involved.

NOTE 3: For users or other persons, this definition is restricted to events related to investigational medical devices.

Any significant change in a patient's condition from screening, regardless of causality, is to be considered an AE (unless the change is determined to be a continuation of a pre-existing condition documented in the patient's medical history). A clinically significant worsening in severity, intensity, or frequency of a pre-existing condition may indicate an AE.

Worsening of findings e.g. in biomicroscopy from no findings to finding graded as moderate/severe, or change in grading from mild to severe, may be an indication of an AE. By investigator's judgment, also milder changes can be recorded as AEs.

An elective surgical procedure scheduled or planned prior to study entry is not considered an AE, and the underlying diagnosis for the procedure should be captured in the medical history as a pre-existing condition.

The lack of efficacy of the study treatment for the condition being investigated is not considered an AE unless a clinically significant change is assessed by the investigator.

Patients' answers given to study questionnaires (or changes in these) are not reviewed as basis for occurrence of AEs. However, the investigators will collect information on AEs at each patient contact by asking an open question on the patient's general health.

For this study, the study devices are LARMABAK®, ALOCROSS® and VISMED®. Regardless of causality to the study device, an AE can be an unintended sign temporally associated with the use of study device.

## 11.2.1.2. Device deficiency

Any inadequacy of an investigational medical device related to its identity, quality, durability, reliability, safety or performance. This may include malfunctions, use error, or inadequacy in the information supplied by the manufacturer.

# 11.2.1.3. Adverse Device Effect (ADE)

Adverse event related to the use of an investigational medical device or procedure.

NOTE 1: This includes any adverse event resulting from insufficiencies or inadequacies in the instructions for use, the deployment, the implantation, the installation, the operation, or any malfunction of the investigational medical device.

NOTE 2: This includes any event that is a result of a use error or intentional abnormal use of the investigational medical device.

## 11.2.1.4. Serious Adverse Event (SAE)

Adverse event that:

- a) led to a death, injury or permanent impairment to a body structure or a body function.
- b) led to a serious deterioration in health of the subject, that either resulted in:
  - a life-threatening illness or injury, or
  - a permanent impairment of a body structure or a body function, or
  - in-patient hospitalization or prolongation of existing hospitalization, or
  - in medical or surgical intervention to prevent life threatening illness
- c) led to foetal distress, foetal death or a congenital abnormality or birth defect.

NOTE 1: Planned hospitalization for pre-existing condition, or a procedure required by the Clinical Investigation Plan (CIP), without a serious deterioration in health, is not considered a serious adverse event.

# 11.2.1.5. Serious Adverse Device Effect (SADE)

Adverse device effect that has resulted in any of the consequences characteristic of a serious adverse event. A SADE is device or procedure related.

## 11.2.1.6. Unanticipated Serious Adverse Device Effect (USADE)

Serious adverse device effect which by its nature, incidence, severity or outcome has not been identified in the current version of the risk analysis report. An USADE is device or procedure related.

NOTE 1: Anticipated SADE (ASADE): an effect which by its nature, incidence, severity or outcome has been previously identified in the risk analysis report. The ASADE shall be documented in the CIP, the Instruction For Use (IFU) and the informed consent form.

NOTE 2: This enables compliance with any reporting requirements for anticipated and unanticipated SADEs.

#### 11.2.1.7. Serious Ocular Adverse Events

Serious ocular adverse events include, but are not limited to the following adverse events which are considered to be sight-threatening and are to be reported as SAEs (medically important criteria):

- Adverse Events that cause a decrease in visual acuity > 6 lines (compared with the last assessment of visual acuity at the last visit)
- Adverse Events that cause a decrease in visual acuity to the level of Light Perception or worse
- Adverse Events that required surgical intervention or laser to prevent permanent loss of Sight
- Adverse Events associated with severe intraocular inflammation (i.e. 3+ anterior chamber cell/flare or 3+ vitritis)
- Corneal perforation
- Adverse Events that, in the opinion of the investigator, may require medical intervention to prevent permanent loss of sight

#### 11.2.2. Assessment of Adverse Events

All AEs (non-serious and serious) spontaneously reported by the patient and/or in response to an open question from the study personnel or revealed by observation will be recorded and assessed during the study at the investigational site. Regardless of relationship to the clinical study, all AEs that occur at any time from the point of signing of ICF to participate in the study until patient withdrawal or the scheduled exit visit must be recorded.

Information about all AEs will be collected from the signing of consent form until the end of the study. Even after completion of the study, the investigator shall notify ITEC services of any new SAEs that may be associated with the study device.

Non-serious AEs will be evaluated until recovery or until the last study visit. The investigator must follow-up with the patients with a SAE until it has resolved, stabilized or a final assessment can otherwise be done. The same principle applies to all study device-related AEs which caused early termination.

The investigator will take appropriate and necessary therapeutic measures required for resolution of the AE. Any medication necessary for the treatment of an AE must be recorded. During the investigator masked treatment period, the investigator should only unmask the treatment allocation if this is relevant to the safety of the patient.

During the study, patients will also be allowed to use unpreserved artificial tears provided by the Sponsor. The events with causal relationship to the artificial tears are considered as AEs.

#### 11.2.2.1. Seriousness assessment

The seriousness of each AE must be assessed by the investigator according to the criteria set for SAEs in section 11.2.1.4. If the event does not meet the criteria of a SAE, it is assessed as non-serious

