## 11.2.2.3. Severity of the Adverse Event

Severity (intensity) of the AE will be assessed according to the following scale:

- Mild: awareness of sign or symptom, but easily tolerated
- Moderate: discomfort sufficient to cause interference with normal activities
- Severe: incapacitating, with inability to perform normal activities

It is important to distinguish between serious and severe AEs. Severity is a measure of intensity whereas seriousness is defined by the criteria under Section 11.2.1.4. An AE of severe intensity may not be considered serious.

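### Seriousness is judged against section 11.2.1.4, which lacks the sight-threatening criterion under which section 11.2.1.7 makes ocular events reportable as SAEs

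*Protocol*

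**What the plan says.** Four places in the protocol bear on whether an adverse event is serious.

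- Section 11.2.2.1 is the instruction that the investigator applies: "The seriousness of each AE must be assessed by the investigator according to the criteria set for SAEs in section 11.2.1.4". It adds the default: "If the event does not meet the criteria of a SAE, it is assessed as non-serious".
- Section 11.2.2.3, in separating severity from seriousness, says that "seriousness is defined by the criteria under Section 11.2.1.4". It sets no default of its own.
- Section 11.2.1.4 gives the criteria to which both refer. Criterion (a) is an event that "led to a death, injury or permanent impairment to a body structure or a body function". Criterion (b) is a serious deterioration in health that results in life-threatening illness or injury, permanent impairment, hospitalisation, or "in medical or surgical intervention to prevent life threatening illness". Criterion (c) covers foetal and congenital outcomes.
- Section 11.2.1.7 gives an open-ended list of six kinds of ocular event that "are considered to be sight-threatening and are to be reported as SAEs (medically important criteria". One of the six reads "Adverse Events that required surgical intervention or laser to prevent permanent loss of Sight".

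Section 11.2.1.4 does not refer to 11.2.1.7, and neither 11.2.2.1 nor 11.2.2.3 mentions it.

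**The concern.** Section 11.2.1.7 relies on a medically important criterion that 11.2.1.4 does not contain, and 11.2.1.4 is the only section named in the seriousness instruction. An investigator who follows 11.2.2.1 step by step can therefore grade as non-serious an ocular event that 11.2.1.7 makes an SAE.

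The label matters in several places:

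- Section 5.3.2.2 makes patients with an SAE, and the number of SAEs, safety endpoints. Section 12.7.1 analyses SAEs separately.
- Sections 11.2.3.1 and 11.2.3.3 attach expedited reporting to SAEs. Under 11.2.1.6 a device effect must be serious before it can be an unanticipated serious adverse device effect.
- Section 11.2.2 follows non-serious events until recovery or the last visit, but SAEs until they have resolved, stabilised or been finally assessed. Device-related events that caused early termination get the longer follow-up either way.
- Section 7.8 links emergency unmasking to an SAE.

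This is an eye-drop trial at about 10 centres, so ocular events are the kind for which consistent classification matters most.

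**Working it through.** No arithmetic applies; the documents give no rate for these events. The check takes each type listed in 11.2.1.7, which is an SAE under that section, and asks whether it also meets a criterion in 11.2.1.4.

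| Type in 11.2.1.7 (paraphrased) | Meets 11.2.1.4? |
|---|---|
| 1. Visual acuity falls by more than 6 lines | Yes if permanent; not if it recovers |
| 2. Visual acuity falls to light perception or worse | Yes if permanent; not if it recovers |
| 3. Surgery or laser was needed to avert permanent sight loss | Not by the intervention criterion, which is limited to life-threatening illness |
| 4. Severe (3+) intraocular inflammation | Not as such |
| 5. Corneal perforation | Arguably yes, as injury under criterion (a) |
| 6. Investigator thinks intervention may be needed to avert permanent sight loss | No |

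Any of the six meets 11.2.1.4 if the patient is hospitalised because of a serious deterioration in health, or if permanent impairment follows. What remains is a reversible or averted event without hospitalisation. Within that group, types 1, 2, 3, 4 and 6 have no matching criterion: 6 listed − 1 arguably covered = 5.

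Type 3 shows the conflict most sharply. Take a patient treated with outpatient laser whose sight is saved. Section 11.2.1.7 names this event as an SAE. Under 11.2.1.4 nobody died, no impairment is permanent, there was no admission, and the illness averted was not life-threatening. Unless injury in criterion (a) is read broadly, no criterion is met and the default in 11.2.2.1 makes the event non-serious.

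**The case against.** The best defence is that a specific, mandatory list supplements a general definition. Section 11.2.1.7 stands in the same definitions block as 11.2.1.4 and says outright that the events are to be reported as SAEs. The default sentence in 11.2.2.1 speaks of SAE criteria without a section number, and nowhere does the protocol say that 11.2.1.4 applies alone. In addition, injury in criterion (a) is not qualified as permanent, so a broad reading would bring in more of the list. A careful site may well reach the intended result in this way.

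That defence makes a sensible reading available, but it does not remove the conflict. The sentence just before the default names 11.2.1.4, section 11.2.2.3 names it again, and no passage brings 11.2.1.7 in. The protocol leaves each site to make the repair.

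Three stronger readings are tempting, and the text does not support them:

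- *All sight-threatening events become non-serious.* They do not. Permanent visual loss, hospitalised cases and arguably corneal perforation already meet 11.2.1.4.
- *Two sections order a non-serious grading.* Only 11.2.2.1 does. Section 11.2.2.3 is an explanatory note.
- *The efficacy conclusion is at risk.* It is not. The SAE summaries are descriptive, and the staining-score comparison, its margin and the sample size do not depend on seriousness.

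**Conclusion.** The inconsistency is real but narrow. Up to five of the six listed ocular event types can be SAEs under 11.2.1.7 and non-serious under 11.2.2.1, and only when the event is reversed or averted without hospitalisation. This rests on a literal reading of the cross-references and an ordinary, not expansive, reading of injury; a broader reading lowers the count. It covers the listed types only, since 11.2.1.7 leaves its list open.

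The practical size is small. With 80 patients planned, few such events are likely, although the protocol gives no rate from which to estimate a number. Each one could still change the SAE count, the reporting duty and the follow-up at the site concerned. This is an inconsistency in safety definitions, worth correcting because the correction is simple; it does not threaten the trial's main conclusion.

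**What to change.** Reconcile sections 11.2.1.4, 11.2.1.7, 11.2.2.1 and 11.2.2.3 so that one set of seriousness criteria applies. The most economical wording is a line in 11.2.1.4 stating that an event in the 11.2.1.7 list also counts as serious. This gives effect to what 11.2.1.7 already orders, and the references to 11.2.1.4 in 11.2.2.1 and 11.2.2.3 then need no change. The sponsor should confirm that this is the intended rule, because emergency unmasking in 7.8 also turns on SAE status, and should check that the safety management plan cited in 11.2.3.1 uses the same criteria.

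The cost is one added line in a definition, submitted to the ethics committee as section 15.1 requires for any amendment, and a note to sites. If patients have already been enrolled, any ocular events recorded as non-serious should be checked against the 11.2.1.7 list. No visit, measurement, sample size or statistical model changes.

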# 11.2.2.2. Causality assessment

An investigator who is qualified in medicine must make the determination of causality to the study devices and artificial tears provided by the Sponsor for each AE occurred during the study as defined in section 11.2.1.1

The relationship between the use of the medical device (including the medical procedure) and the occurrence of each adverse event shall be assessed and categorized. During causality assessment activity, clinical judgement shall be used and the relevant documents, such as the IFU, the Clinical Protocol or the Risk Analysis Report shall be consulted, as all the foreseeable serious adverse events and the potential risks are listed and assessed there. The presence of confounding factors, such as concomitant medication/treatment, the natural history of the underlying disease, other concurrent illness or risk factors shall also be considered.

The sponsor and the investigators will use the following definitions to assess the relationship of the serious adverse event to the investigational medical device or procedures.

- Not related: relationship to the device or procedures can be excluded when:
  - the event is not a known side effect of the product category the device belongs to or of similar devices and procedures;
  - o the event has no temporal relationship with the use of the investigational device or the procedures;
  - o the serious event does not follow a known response pattern to the medical device (if the response pattern is previously known) and is biologically implausible;
  - o the discontinuation of medical device application or the reduction of the level of activation/exposure when clinically feasible and reintroduction of its use (or increase of the level of activation/exposure), do not impact on the serious event;
  - o the event involves a body-site or an organ not expected to be affected by the device or procedure;
  - the serious event can be attributed to another cause (e.g. an underlying or concurrent illness/ clinical condition, an effect of another device, drug, treatment or other risk factors);
  - o the event does not depend on a false result given by the investigational device used for diagnosis, when applicable;
  - o harms to the subject are not clearly due to use error;
  - In order to establish the non-relatedness, not all the criteria listed above might be met at the same time, depending on the type of device/procedures and the serious event.
- Unlikely: the relationship with the use of the device seems not relevant and/or the event can be reasonably explained by another cause, but additional information may be obtained.
- Possible: the relationship with the use of the investigational device is weak but cannot be ruled out completely. Alternative causes are also possible (e.g. an underlying or concurrent illness/clinical condition or/and an effect of another device, drug or treatment). Cases were relatedness cannot be assessed or no information has been obtained should also be classified as possible.

- Probable: the relationship with the use of the investigational device seems relevant and/or the event cannot reasonably explain by another cause, but additional information may be obtained.
- Causal relationship: the serious event is associated with the investigational device or with procedures beyond reasonable doubt when:
  - o the event is a known side effect of the product category the device belongs to or of similar devices and procedures;
  - o the event has a temporal relationship with investigational device use/application or procedures;
  - o the event involves a body-site or organ that
    - the investigational device or procedures are applied to;
    - the investigational device or procedures have an effect on;
  - o the serious event follows a known response pattern to the medical device (if the response pattern is previously known);
  - o the discontinuation of medical device application (or reduction of the level of activation/exposure) and reintroduction of its use (or increase of the level of activation/exposure), impact on the serious event (when clinically feasible);
  - other possible causes (e.g. an underlying or concurrent illness/ clinical condition or/and an effect of another device, drug or treatment) have been adequately ruled out;
  - o harm to the subject is due to error in use;
  - o the event depends on a false result given by the investigational device used for diagnosis, when applicable;
  - o In order to establish the relatedness, not all the criteria listed above might be met at the same time, depending on the type of device/procedures and the serious event.

The sponsor and the investigators will distinguish between the serious adverse events related to the investigational device and those related to the procedures (any procedure specific to the clinical investigation). An adverse event can be related both to procedures and the investigational device. Complications of procedures are considered not related if the said procedures would have been applied to the patients also in the absence of investigational device use/application.

In some particular cases the event may be not adequately assessed because information is insufficient or contradictory and/or the data cannot be verified or supplemented. The sponsor and the Investigators will make the maximum effort to define and categorize the event and avoid these situations. Where the sponsor remains uncertain about classifying the serious event, it should not exclude the relatedness and classify the event as "possible".

Particular attention shall be given to the causality evaluation of unanticipated serious adverse (device) events. The occurrence of USADE could suggest that the clinical investigation places subjects at increased risk of harm than was to be expected beforehand.

